5.7 Accountability of Protocol-specified Treatment

The site is responsible for the return or destruction of investigational product supplied by the sponsor, as required. Authorization for on-site destruction of investigational product that has not been dispensed to a patient (eg, expired investigational product), must be requested from the sponsor prior to destruction. All investigational product containers must be accounted for prior to their destruction at the study site, according to institutional procedures for disposal of hazardous materials. Unused and returned investigational product and containers should be destroyed on-site if possible. If on-site destruction is not possible, supply should be returned to the drug depot, following the sponsor's instructions.

During the study and at completion of the study, the number of investigational product units and containers received, dispensed, returned, and destroyed must be recorded and reconciled.

6 PRIOR AND CONCOMITANT THERAPY

Medications taken, procedures performed (eg, thoracentesis, etc.), and supportive care given during the study will not be documented in the eCRF.

6.1 Supportive Care

Supportive care (eg, antiemetics; analgesics for pain control; growth factors, etc) may be used at the investigator's discretion and in accordance with institutional procedures.

6.2 Anticancer or Experimental Therapy

No other anticancer therapy (including chemotherapy, radiation, antibody or other immunotherapy, gene therapy, vaccine therapy, angiogenesis inhibitors, or other

experimental drugs) of any kind will be permitted while the patient is receiving treatment with rucaparib, with the exception of palliative radiotherapy.

6.3 Radiotherapy

Palliative radiotherapy is permitted during the study. Treatment with rucaparib should be held prior to initiation of radiation therapy and until the patient has recovered from any radiation-related toxicity.

6.4 CYP450 Isoenzyme Inhibitors, Inducers, and Substrates

Based on the results from the in vivo cytochrome P450 (CYP) interaction study (CO-338-044), rucaparib is a moderate inhibitor of CYP1A2, and a weak inhibitor of CYP2C9, CYP2C19, and CYP3A. Caution should be used in patients on rucaparib taking concomitant medicines that are sensitive clinical substrates of CYP1A2, CYP2C9, CYP2C19, and/or CYP3A (see Appendix 1).

Although in vitro rucaparib metabolism mediated by CYP3A4 was slow, a significant contribution of CYP3A4 in vivo cannot be excluded. Caution should be used for concomitant use of strong CYP3A4 inhibitors or inducers.

6.5 Anticoagulants

Rucaparib is a weak inhibitor of CYP2C9 in vivo. Caution should be exercised in patients receiving rucaparib and concomitant warfarin (Coumadin). Patients taking warfarin should have international normalized ratio (INR) monitored regularly per standard clinical practice.

6.6 Other Concomitant Medications

Therapies considered necessary for the patient's well-being may be given at the discretion of the investigator. Herbal and complementary therapies are discouraged because of unknown side effects and potential drug interactions.

Rucaparib marginally increased digoxin area under the concentration-time curve (AUC) by 20%. Caution should be exercised for patients receiving rucaparib and requiring concomitant medication with digoxin. Patients taking digoxin should have their digoxin levels monitored after starting rucaparib and then regularly per standard clinical practice.

In vitro, rucaparib is a potent inhibitor of multidrug and toxin extrusion (MATE1) and MATE2-K, a moderate inhibitor of organic cation transporter (OCT)1, and a weak inhibitor of OCT2. As inhibition of these transporters could decrease metformin renal elimination and decrease liver uptake of metformin, caution is advised when metformin is co-administered with rucaparib. In addition, rucaparib is an inhibitor of the breast cancer resistance protein (BCRP) with a concentration at which 50% maximal inhibitory response is observed (IC50) value suggesting potential BCRP inhibition and increased exposures of medicinal products that are BCRP substrate (eg, rosuvastatin).

6.7 General Restrictions

Photosensitivity has been observed in patients treated with rucaparib. Patients should avoid spending time in direct sunlight because they burn more easily during treatment with rucaparib. When outdoors, patients should use typical precautions such as applying sunscreen (sun protection factor 50 or greater) and/or covering exposed skin with clothing and wearing a hat and sunglasses.

7 STUDY PROCEDURES AND METHODS

7.1 Schedule of Assessments

Table 7-1 summarizes the procedures and assessments to be performed for all patients.

Study procedures and assessments should be performed as close as possible to the scheduled time.

Table 7-1Schedule of Assessments

	Prior to EOT in Parent Study	Treatment Phase	Post-Treatment Phase	
Procedure ^a		Cycle X Day 1	Post-treatment Follow-up ^b	Long-term Follow-up ^c
Informed Consent ^d (Section 7.2)	X			
Adverse Events ^e (Sections 8.6 and 8.7)		The Investigator should monitor and educate patients on possible AEs observed with rucaparib; only SAEs and AESIs will be reported in Clovis PV database		Х
Complete Blood Count		Institutional standard of care practices per Investigator		
Clinical Chemistry, Urinalysis, Vital Signs		Institutional standard of care practices per Investigator		
Pregnancy Test ^f (WOCBP only) (local lab) (Section 7.3.2.2)		Х	Х	
Disease Assessments (Section 7.3.1)		Institutional standard of care practices per Investigator		
Rucaparib Dispensation/Administration/Accountability ^g (Section 5.7)		Х	Х	
Long-term Follow-up Data Collection (Section 7.3.3)				Х

Abbreviations: AE = adverse event; AESI = adverse event of special interest; AML = acute myeloid leukemia; eCRF = electronic Case Report Form; EOT = end of treatment; LTFU = long-term follow-up; MDS = myelodysplastic syndrome; PV = pharmacovigilance; SAE = serious adverse event, WOCBP = women of childbearing potential.

^a Treatment cycles are 28 days. Unless otherwise specified, all assessments are to be completed as close as possible to the scheduled time point. Data to be entered in the appropriate electronic Case Report Form (eCRF) include enrollment, dosing, discontinuation, survival/death, and long-term follow-up (LTFU). Dose modifications, hematology/clinical chemistry assessments, and pregnancy testing are not required to be entered.

^b Post-treatment safety follow-up visit should occur approximately 28 days (±7) from the last dose of rucaparib, or can be performed on the date of discontinuation if that date is at least 28 days from last dose.

^c Patients who have discontinued treatment, regardless of reason, and provide consent, should have LTFU data collected approximately every 12 weeks relative to the last dose of rucaparib until death, loss to follow-up, withdrawal of consent, or study closure, as applicable based on parent study objectives. This data will be captured in the eCRF.

Table 7-1 Schedule of Assessments

- ^d Patients rolling over to continued treatment with rucaparib in this study will sign consent prior to the End-of-Treatment (EOT) Visit of the parent study. Patients rolling over from LTFU in the parent study will sign consent prior to the first LTFU visit in the rollover study.
- ^e Adverse events (AEs) will be monitored but only serious AEs (SAEs)/adverse events of special interest (AESIs) are collected per Clovis Pharmacovigilance (PV) guidelines and reported in the Clovis PV database through 28 days after last dose of rucaparib (Post-treatment Follow-up Visit). Ongoing SAEs and AESIs at the time of the Post-treatment Follow-up Visit will be followed to resolution, stabilization, or lost to follow-up. After this visit, only SAEs considered as potentially related to study drug (including serious reports of pneumonitis or associated events, if considered to be related to study drug), and AESIs of MDS and AML irrespective of causality, will be reported. If a patient discontinues from treatment in the rollover study and begins a subsequent anticancer therapy, the sponsor will terminate collection of SAEs.
- ^f Women of childbearing potential (WOCBP) must have a negative pregnancy test result ≤ 3 days prior to the first dose of rucaparib in this study. A pregnancy test must be performed ≤3 days prior to Day 1 of every cycle from Cycle 2 and beyond during the treatment phase. Testing may be performed per institutional standard of care during treatment, and results must be reviewed prior to commencing a new cycle of rucaparib. A pregnancy test must be performed at the EOT Visit of the parent study and the Post-treatment Follow-up Visit of the rollover study. See Section 8.5 for reporting a positive pregnancy result.
- ^g More than 1 cycle of rucaparib can be dispensed, if deemed appropriate by investigator. Patients will be instructed to bring their rucaparib tablets and all containers (empty, partially used, and/or unopened) to each scheduled visit for reconciliation by site personnel.

7.2 Informed Consent Timing

Informed consent must be obtained from each patient prior to entering the rollover study. General aspects of informed consent are described in Section 10.2.1 and the informed consent process is described in Section 10.2.2. Informed consent can be obtained in written format, as possible. For patients in active treatment in the parent study, informed consent can be obtained prior to the EOT Visit in the parent study. For patients in LTFU in the parent study, it is not necessary to repeat the EOT Visit, but informed consent must be obtained before the first LTFU visit in this study.

7.3 Methods of Data Collection

SAEs and AESIs that occur after informed consent will be collected through 28 days after the last dose of rucaparib for patients receiving treatment in this study. Only SAEs/AESIs will be reported in the Clovis PV database.

After the 28-day Post-treatment Follow-up Visit, only SAEs considered as potentially related to rucaparib should be reported per Clovis PV requirements and captured in the Clovis PV database. This includes serious reports of pneumonitis or associated events, if considered to be related to study drug.

After the 28-day Post-treatment Follow-up Visit, AESIs of MDS and AML, irrespective of causality, should be reported per Clovis PV requirements and captured in the Clovis PV database.

• AESIs of pneumonitis or associated events should only be reported up to, but not beyond, the Post-treatment Follow-up Visit (28-days after the last dose of rucaparib).

Hematology, clinical chemistry, urinalysis, vital signs, and disease assessments should be performed locally per institutional standard of care practices. Pregnancy testing will be performed locally per institutional standard of care at screening (the EOT Visit of parent study), before initiation of each treatment cycle, and at the Post-treatment Follow-up Visit of this study.

7.3.1 Disease Status Evaluations

Target and non-target lesions will be evaluated for evidence of progression based on institutional standard of care practices for the purpose of determining continued benefit of study treatment. Tumor assessment data will not be entered in the eCRF.

Tumor assessment will be performed according to institutional standard of care practices until disease progression, as assessed by the investigator, discontinuation for reasons other than progression, loss to follow up, withdrawal from study, death, or study closure.

7.3.2 Safety Evaluations

7.3.2.1 Adverse Event Assessment

The investigator has the responsibility for assessing the safety of the patients, including monitoring and management of all AEs experienced, and for compliance with the protocol to ensure study integrity. Only SAEs and AESIs occurring from the time of informed consent through 28 days after the last dose of rucaparib will be reported in the Clovis PV database.

After the post-treatment 28-day follow-up window, only SAEs considered as potentially related to study drug should be reported per Clovis PV requirements and captured in the Clovis PV database. This includes serious reports of pneumonitis or associated events, if considered to be related to study drug.

After the 28-day Post-treatment Follow-up Visit, AESIs of MDS and AML, irrespective of causality, should be reported per Clovis PV requirements and captured in the Clovis PV database.

• AESIs of pneumonitis or associated events should only be reported up to, but not beyond, the Post-treatment Follow-up Visit (28-days after the last dose of rucaparib).

Any ongoing SAEs and AESIs will be followed until resolution or stabilization.

If a patient discontinues from treatment in the rollover study and begins a subsequent anticancer therapy, the sponsor will terminate collection of SAEs.

Complete details for monitoring AEs, including the definition of drug-related AEs, are provided in Section 8.

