5.5.1.2 Management of new or worsening pulmonary symptoms

If new or worsening unexplained pulmonary symptoms suggestive of pneumonitis (including, but not limited to, dyspnea) occur, or a deterioration of pulmonary function is observed, and/or radiologic abnormality is detected in the lungs, and this occurs in the absence of any clear diagnosis, a diagnostic workup (including high resolution computed tomography [CT] scan) in consultation with a pulmonologist should be performed in order to rule out pneumonitis. During this time, treatment with rucaparib may be interrupted or continued per investigator discretion.

Following investigation, if pneumonitis is not confirmed, treatment with rucaparib may be resumed/continued as deemed appropriate by the investigator and in accordance with the study protocol directions for management of AEs. All confirmed events of pneumonitis should be treated as appropriate per medical judgement and institutional guidelines. If the event resolves and retreatment with rucaparib is being considered, please consult the study Medical Monitor. Retreatment with rucaparib may be resumed at the current or a reduced dose, if appropriate.

Refer to Sections 8.3 and 8.6 of the protocol for additional information regarding classification and reporting of pneumonitis (and related events) as an AESI.

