8.3 Definition of an Adverse Event of Special Interest

Adverse events of special interest (AESIs, serious or nonserious) are defined as AEs of scientific and medical concern specific to the sponsor's product or program, for which ongoing monitoring and rapid communication by the investigator to the sponsor can be appropriate. Such an event might warrant further investigation in order to characterize and understand it. Depending on the nature of the event, rapid communication by the study sponsor to other parties (eg, regulators) might also be warranted.

Details on the sponsor's currently agreed list of AESIs for rucaparib can be found in the current rucaparib IB. These AESIs are to be reported to the sponsor **within 24 hours** of knowledge of the event (see Section 8.6 for reporting instructions).

Report any AE of pneumonitis, or any of the following AEs, irrespective of causality assessment and severity, as an AESI within 24 hours using the study Serious Adverse Event Form and the applicable procedures as outlined in Section 8.6:

- Pneumonitis
- Interstitial lung disease
- Pulmonary fibrosis
- Acute interstitial pneumonitis
- Alveolitis necrotizing
- Alveolitis
- Hypersensitivity pneumonitis
- Organizing pneumonia

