8.6 Recording of Serious Adverse Events and Adverse Events of Special Interest

Any SAE/AESI that occurs after signing informed consent through 28 days after receiving the last dose of investigational product is to be reported to the sponsor and captured in the PV database.

After the 28-day Post-treatment Follow-up Visit, only SAEs assessed as potentially related to study drug should be reported per Clovis PV requirements and captured in the Clovis PV database. This includes serious reports of pneumonitis or associated events, if considered to be related to study drug.

After the 28-day Post-treatment Follow-up Visit, AESIs of MDS and AML, irrespective of causality, should be reported per Clovis PV requirements and captured in the Clovis PV database.

• AESIs of pneumonitis or associated events should only be reported up to, but not beyond, the Post-treatment Follow-up Visit (28-days after the last dose of rucaparib).

Information on the follow-up of SAEs, and AESIs is provided in Section 8.7.

In order to avoid vague, ambiguous, or colloquial expressions, the AE should be recorded in standard medical terminology rather than the patient's own words. Whenever possible, the investigator should combine signs and symptoms that constitute a single disease entity or syndrome into a final diagnosis, if appropriate. For example, fever, cough, and shortness of breath may be reported as pneumonia, if that is a reasonable diagnosis.

Each SAE is to be evaluated for causal relationship to the investigational drug, severity, and seriousness. The action taken, and the outcome must also be recorded.

SAEs and AESIs that occur during the study or within 28 days after receiving the last dose of investigational product, whether or not related to investigational product, must be reported immediately (ie, **within 24 hours** of knowledge of the event or additional information for a previously-reported event) to the sponsor/SAE designee. The contact information for reporting of SAEs/AESIs can be found on the SAE/AESI Reporting Form.

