8.6.1 Onset Date of Serious Adverse Events and Adverse Events of Special Interest

The onset date is the date that the event or the signs/symptoms attributed to the event started.

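### The pneumonitis AESI cut-off limits the date of reporting and is tied to the follow-up visit, while the AESI window runs on occurrence through 28 days after the last dose, so a nonserious case recognised late is both required and barred

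*Protocol*

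**What the plan says.** **Window by occurrence.** Protocol Section 7.3.2.1, on entry into the pharmacovigilance database: "Only SAEs and AESIs occurring from the time of informed consent through 28 days after the last dose of rucaparib will be reported". Section 8.6, on reports to the sponsor: "Any SAE/AESI that occurs after signing informed consent through 28 days after receiving the last dose of investigational product is to be reported". Section 8.6 sets the deadline at 24 hours "of knowledge of the event or additional information for a previously-reported event", regardless of causality.

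**Definition.** Section 8.3: "Report any AE of pneumonitis, or any of the following AEs, irrespective of causality assessment and severity, as an AESI within 24 hours". The list that follows consists of diagnoses, such as interstitial lung disease and organizing pneumonia.

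**Onset.** Section 8.6.1: "The onset date is the date that the event or the signs/symptoms attributed to the event started".

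**Cut-off by reporting.** Sections 3.2.2, 7.3, 7.3.2.1 and 8.6 carry the same bullet: "AESIs of pneumonitis or associated events should only be reported up to" the Post-treatment Follow-up Visit, with an underlined statement that reporting does not go past it. The bullet describes that visit as 28 days after the last dose.

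**Visit timing.** Section 3.2.2 and Table 7-1 (footnote b) place the visit at about 28 days after the last dose, plus or minus 7.

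**What survives the visit.** SAEs judged potentially related remain reportable, including serious related pneumonitis. So do MDS and AML whatever the cause. SAEs and AESIs ongoing at the visit continue to be followed.

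**The concern.** The general rule asks when the event happened. The bullet asks when the report is made. The two agree only if every case is recognised by the visit. Pneumonitis need not be: Section 5.5.1.2 describes unexplained pulmonary symptoms for which "a diagnostic workup (including high resolution computed tomography [CT] scan) in consultation with a pulmonologist should be performed" before the diagnosis is settled. Any delay between first symptoms and recognition that spans the visit sets the two rules against each other.

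Collecting SAEs and AESIs is one of the three objectives in Section 2. Section 9.4 plans no safety analyses, so the individual report to the pharmacovigilance database is the study's safety output. Two sites with the same late-recognised case could each follow the protocol, and one would report it while the other would not.

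**Working it through.** The protocol states no figure on this point to reproduce. The check sets the rules side by side and does day arithmetic, counting days from the last dose.

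**1. A late-recognised case (dates assumed for illustration).** Symptoms on day 20, visit on day 28, nonserious pneumonitis confirmed on day 36.
- Onset under Section 8.6.1: day 20. Since 20 ≤ 28, the event is inside the window of Sections 7.3.2.1 and 8.6.
- Reporting clock under Section 8.6: it starts at knowledge on day 36, so a report is due within 24 hours.
- The bullet: the last permitted reporting day is the visit, day 28. Knowledge comes 36 − 28 = 8 days too late, so no AESI report should be made.
- Result: required by one rule and barred by the other. Section 8.6 contains both.

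**2. Does another rule capture this case?**
- Serious and related: yes, as an SAE after the visit.
- Serious, any causality, onset in the window: the duty in Section 8.6 covers SAEs regardless of relationship, so the point is not rested on these.
- Nonserious: no. Only SAEs and AESIs go to the pharmacovigilance database, and the eCRF items listed in Section 10.5 (enrollment, dosing, discontinuation, survival/death, long-term follow-up) include no nonserious adverse events.
- Follow-up of AESIs ongoing at the visit: this helps only if an AESI has already been identified. Unexplained dyspnea still under investigation is not on the Section 8.3 list.

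**3. Does reading the bullet as an onset limit remove the conflict?** The visit falls between 28 − 7 = day 21 and 28 + 7 = day 35.

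| Visit day | Onset days in dispute | 28-day window | Visit-based limit |
|---|---|---|---|
| 21 | 22 to 28 (7 days) | inside | outside |
| 28 | none | agree | agree |
| 35 | 29 to 35 (7 days) | outside | inside |

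Even on this reading the limits can differ by up to 7 days in either direction. Footnote b of Table 7-1 also lets the visit take place on the date of discontinuation when that is at least 28 days after the last dose. It states no upper bound for that case, which is not counted in the 7 days.

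**The case against.** The best defence is that the bullet is a loosely worded onset limit. It carries its own gloss of 28 days after the last dose, which repeats the occurrence window. It also follows the sentences on which event types stay collectable after the visit, where it contrasts pneumonitis with MDS and AML. On that reading it says which events count, not when a form may be sent, and Section 8.6 settles the day-20 example in favour of reporting. In addition, a patient with symptoms on day 20 will normally be seen at the visit. If pneumonitis is already suspected and reported by then, later confirmation is additional information on a reported event.

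Much of this stands. The onset reading is plausible and may be what was meant, and a suspicion reported in time avoids the problem. Two things remain. The underlined text is about reporting, in all four places, and a site that obeys it literally does nothing wrong. And the onset reading leaves the 7-day mismatch between the actual visit and day 28.

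A reader might also infer that the pulmonary work-up is mandatory and so guarantees a delay. Section 5.5.1.2 says only that it should be done, sits among the dose-modification rules and gives no duration. The point does not need it: any delay between onset and recognition is enough.

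**Conclusion.** The point holds for nonserious pneumonitis and the associated diagnoses with onset inside the 28-day window and recognition after the visit. For these the protocol gives opposing instructions and no other route of capture. Separately, the visit-based and day-based limits can differ by up to 7 days under the plus or minus 7 visit window. This is a modest wording defect. With no safety analysis planned, no planned rate or comparison is biased; what is at stake is whether individual AESI reports are made consistently.

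Two stronger conclusions are tempting but not supported.
- *A percentage of cases lost.* An assumed 7 to 14 day work-up gives 7/28 = 25% to 14/28 = 50%, but that is a share of the days in the post-dose window, not of cases. The reporting period runs from consent through all treatment plus 28 days, and the protocol gives neither a lag nor an expected number of cases. No percentage should be quoted.
- *The same problem for MDS at study entry.* A reader might infer that MDS diagnosed here, with cytopenia dating from the parent study, is excluded by its onset date. No sentence bars reporting of MDS or AML, and the rule after the visit is open-ended and independent of causality. Section 8.6.1 says which date to record and does not make it a test of reportability. The parent studies' reporting rules are not in the document, so a loss of such cases cannot be shown.

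**What to change.** Reconcile the four copies of the bullet (Sections 3.2.2, 7.3, 7.3.2.1 and 8.6) with the occurrence window by stating the cut-off on onset with one anchor, for example: *pneumonitis AESIs with onset through 28 days after the last dose are reported whenever they become known*. Leave the rule on serious related pneumonitis after the visit as it is. Align footnote e of Table 7-1, which likewise treats the visit and 28 days as the same point.

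The cost is wording only, with no new assessments or visits. The downside is a few more AESI reports, some of them after the visit.
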